**Assessment of Quality of Life Changes on Lower Extremity
Lymphedema Patients using an Advanced Pneumatic
Compression Device at Home.**

Protocol# 5010

**03 July 2019
Protocol Version 3.1**

Investigator Signature

Protocol Title: Assessment of Quality of Life Changes on Lower Extremity Lymphedema Patients using a Pneumatic Compression Device at Home.

Protocol Number: 5010

Date: 03 July 2019, Version 3.1

I confirm that I have read this protocol. I will comply with the protocol and the principles of Good Clinical Practices (GCP), institutional research policies and procedures and other appropriate regulatory requirements.

Site Principal Investigator Name (Print)

Site Principal Investigator Signature

Date

SYNOPSIS

Title of Study	Assessment of Quality of Life Changes on Lower Extremity Lymphedema Patients using an Advanced Pneumatic Compression Device at Home.
Protocol Date	3 July 2019
Protocol Version	3.1
Name of Sponsor	Tactile Medical™
Device	Flexitouch® system or Flexitouch® Plus
Primary Endpoint	Quality of life (QoL), lymphedema symptoms, lymphedema and venous related complication rate, lymphedema and venous related unscheduled visits
Secondary Endpoint	Limb circumference changes, Flexitouch compliance, skin changes, QoL
METHODOLOGY	
Study Design	Multi-center, single arm, observational clinical trial
Treatments	Subjects will be instructed to use the Flexitouch system or Flexitouch Plus as prescribed and will be followed for 52 weeks. The subjects will be seen in clinic 4, 8, 12, 24 and 52 weeks after completion of device training. The subject will also have phone call follow-ups at 1, 18, 32 and 40 weeks after device training.
Treatment Duration	As prescribed
SUBJECT POPULATION	
Number Planned	300
Inclusion Criteria	
 1) Age 18 or older 2) Diagnosis of primary or secondary, unilateral or bilateral, LE lymphedema 3) Ability and willingness to participate in all aspects of the study including following prescribed care 4) Ability to provide informed consent 5) Must have a prescription for the Flexitouch (Flexitouch system or Flexitouch Plus)
Exclusion Criteria	
 1) Diagnosis of active or recurrent cancer, or less than 3 months at the time of initial evaluation from the completion of chemotherapy, radiation therapy or primary surgery for the treatment of cancer. 2) Active skin or limb infection/inflammatory disease (acute cellulitis, or other uncontrolled skin or untreated inflammatory skin disease) 3) Acute thrombophlebitis (in last 2 months) 4) Pulmonary embolism within the previous 6 months 5) Deep Vein Thrombosis (DVT) within the previous 3 months 6) Severe peripheral artery disease (critical limb ischemia including ischemic rest pain, arterial wounds, or gangrene) 7) Pulmonary edema 8) Heart failure (acute pulmonary edema, decompensated acute heart failure) 9) Patients with poorly controlled asthma 10) Previous use of the study pneumatic compression device (PCD) 11) Currently using multi-layer bandaging (MLB) unless bandages can be removed for limb circumference measurements 12) Pregnant women or women of childbearing potential not on contraception 13) Any condition where increased venous and lymphatic return is undesirable 14) Currently participating in another medical device or drug clinical trial 15) Signs of noncompliance at the week 4 visit, including: using the device less than 3 times per week and/or not attending the scheduled visit

Table of Contents

Investigator Signature..... 2

SYNOPSIS..... 3

1.0 Contact Information..... 7

 1.1 Sponsor Contact Information..... 7

 1.2 Study Principal Investigator Information 7

2.0 Abbreviations 7

3.0 Introduction 7

 3.1 Background and Rationale 7

 3.2 Device Description 8

4.0 Study Objectives 8

5.0 Study Design..... 8

 5.1 Study Endpoints 9

 5.1.1 Primary Endpoints..... 9

 5.1.2 Secondary Endpoints 9

 5.2 Subject Selection..... 10

 5.2.1 Inclusion Criteria 10

 5.2.2 Exclusion Criteria..... 10

 5.2.3 Subject Withdrawal or Early Termination..... 11

 5.3 Dosage and Rationale 11

 5.4 Study Timetable 11

6.0 Study Visit Summaries 11

 6.1 Screening/Baseline Visit..... 11

 6.2 Week 0/Training..... 12

 6.3 Weeks 1 (+7 days), 18, 32, & 40 (± 14 days) Follow-up Phone Calls..... 12

 6.4 Weeks 4, 8, 12 (± 7 days), 24, and 52 (± 14 days) In-Clinic Follow-Up Visit(s)..... 12

7.0 Study Procedures 12

 7.1 Informed Consent 12

 7.2 Demographics & Medical History 13

 7.3 Vital Signs 13

 7.4 Skin Assessment..... 13

7.4.1	Fibrosis Grading	13
7.4.2	Assessment of Skin Changes	13

2.0 Abbreviations

CFR	Code of Federal Regulations
CRA	Clinical Research Associate
CRF	Case Report Form
DVT	Deep Vein Thrombosis
ER	Emergency Room
FDA	Food and Drug Administration
GCP	Good Clinical Practice
HCU	Health Care Utilization
IC	Informed Consent
IRB	Institutional Review Board
LE	Lower Extremity
MLB	Multi-Layer Bandaging
PCD	Pneumatic Compression Device
QoL	Quality of Life
SAE	Serious Adverse Event
SF-36	Short Form-36

3.0 Introduction

3.1 Background and Rationale

The purpose of this study is to evaluate the effect of an advanced pneumatic compression device in improving symptoms and quality of life in patients with lower extremity lymphedema.

Lymphedema is a chronic and disfiguring disease usually secondary to excessive fluid and protein accumulation in the interstitium as result of lymphatic system obstruction.¹ It can occur either primarily (as a result of congenital malformations)

or secondarily (as a result of trauma to the lymphatic system, surgery, radiation therapy, obesity and chronic venous insufficiency).^{2,3} This leads to limb swelling in early stages with progression to thickening skin and fibrosis leaving the affected extremity susceptible to skin breakdown and repeated infections. There is no cure for lymphedema, and the available treatment modalities consist of manual lymphatic drainage, compression therapy, and in very severe cases lymphatic exchange, a costly and invasive procedure.⁴

Pneumatic Compression Devices (PCDs) offer a novel modality for treatment of lymphatic obstruction. The Flexitouch[®] System and Flexitouch[®] Plus are PCDs that target all major lymphatic beds and release pressure in a systematic manner, mimicking a functional drainage system.⁵ Prior studies demonstrated improvement in control of edema and ease of use; however improvement in quality of life (QoL) and decrease in symptoms has not been thoroughly evaluated.^{6,7,8} Therefore we propose to demonstrate improved QoL and symptoms in patients with lower extremity (LE) lymphedema.

3.2 Device Description

The Flexitouch system and Flexitouch Plus (Tactile Medical[™], Minneapolis, MN, USA) are segmental, programmable, gradient PCDs which have been cleared by the Food and Drug Administration (FDA) for market in the US (K013061), (US HCPCS code E0652). The devices consist of a controller and garment set. The garments are constructed of nylon and have 27-32 chambers, depending upon garment size. The pressure setting is variable between “normal” and “increased.” The Flexitouch system and Flexitouch Plus are intended for the treatment of lymphedema, primary lymphedema, post mastectomy edema, edema following trauma and sports injuries, post immobilization edema, venous insufficiencies, reducing wound healing time and assistance in healing stasis dermatitis, venous stasis ulcers, or arterial and diabetic leg ulcers.

The Flexitouch Plus is functionally equivalent to the Flexitouch system, however it permits bilateral treatment of the lower extremities, incorporates a color display with larger buttons on the controller, and provides more comfortable garments that are easier to put on and take off.

4.0 Study Objectives

The study will assess QoL, lymphedema symptoms, lymphedema and venous related complication rate, lymphedema and venous related unscheduled visits, Flexitouch compliance, and skin and limb circumference changes in primary or secondary, unilateral or bilateral, lower extremity lymphedema patients using the Flexitouch system or Flexitouch Plus during the 52 week study period.

5.0 Study Design

This investigation is a post-market, on label, multi-center, single arm, observational clinical trial of a prospective cohort of 300 subjects with primary or secondary, unilateral or bilateral, lower extremity lymphedema in the United States. All subjects will receive PCD treatment for 52 weeks (*Figure 1*).

[figure not shown]

Figure 1. Study Design

5.1 Study Endpoints

5.1.1 Primary Endpoints

The following primary endpoints for this study will compare changes after 12 weeks of treatment to baseline for the following parameters:

- QoL
- Lymphedema symptoms

In addition, the number of occurrences after 52 weeks of treatment will be compared to the number of occurrences in the year preceding treatment for the following variable:

- Lymphedema and venous related health care utilization

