5.2 Subject Selection

5.2.1 Inclusion Criteria

1. Age 18 or older
2. Diagnosis of primary or secondary, unilateral or bilateral, LE lymphedema
3. Ability and willingness to participate in all aspects of the study including following prescribed care
4. Ability to provide informed consent
5. Must have a prescription for the Flexitouch (Flexitouch system or Flexitouch Plus)

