7.2 Demographics & Medical History

Demographics will be collected at baseline including the date of birth, ethnicity, race, gender, and employment status.

If the subject is female and of childbearing potential, a urine pregnancy test will be performed to ensure the subject is not pregnant. Per exclusion criterion 11, if a subject is pregnant or a women of childbearing potential not on contraception, they will be excluded from the study.

Significant medical history and lymphedema history will be collected at baseline including number of lymphedema and venous related visits that required health care utilization (HCU) (includes clinic visits, hospitalization, walk-in clinic/urgent care, and ER visits).

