7.12 Flexitouch Administration & Training

After the subject's screening/baseline visit, Tactile Medical personnel will perform in-home device training. The date of device training (Day 0) will be used to determine the timing of subsequent follow-up visits.

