8.0 Study Device Accountability

To participate in the study, the Flexitouch must be covered by a payer. The Flexitouch will be provided to the subject and tracked according to normal business practices. Subjects' whose payer requires rental of the Flexitouch will be excluded from the study.

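### The prior-year HCU total includes the prescribing visit and any run-up to it, so the single-arm comparison can show a reduction with no device effect

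*Combined protocol and SAP*

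**What the plan says.** Section 5.1.1 lists lymphedema and venous related HCU as a primary endpoint: "the number of occurrences after 52 weeks of treatment will be compared to the number of occurrences in the year preceding treatment". Section 5.0 describes a "post-market, on label, multi-center, single arm, observational clinical trial", so each subject's own prior year is the only comparator.

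Entry depends on a prescribing decision. Section 5.2.1, criterion 5, reads "Must have a prescription for the Flexitouch (Flexitouch system or Flexitouch Plus", and Section 8.0 adds "To participate in the study, the Flexitouch must be covered by a payer". Neither section sets a threshold for severity or recent visits. The clock starts later, at training, which follows the baseline visit. Section 7.12 says: "The date of device training (Day 0) will be used to determine the timing of subsequent follow-up visits".

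The two counts are collected differently. Section 7.2 takes the prior count as history at baseline: "number of lymphedema and venous related visits that required health care utilization (HCU) (includes clinic visits", together with hospital, urgent care and emergency visits. It asks for a number and not for dates. Section 7.11 assesses on-treatment HCU at every phone call and clinic follow-up, which the schedule in 7.13 puts at weeks 1, 4, 8, 12, 18, 24, 32, 40 and 52.

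Section 13.1 names no test, model or sensitivity analysis. No section provides a washout, a stable period before entry, or separate handling of the prescribing visit.

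**The concern.** A before/after count is vulnerable when the dividing point is chosen because of what happened just before it. Here that point follows a decision to prescribe. If patients tend to be prescribed the device after a spell of extra visits, the prior year holds that spell and the following year need not. Counts then fall through regression to the mean, whatever the device does. The visit at which the prescription was written may add one more prior-year event with no counterpart afterwards.

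A single prior-year total cannot show whether this happened. The endpoint is primary and there is no control arm, so a reader could take such a fall for benefit.

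**Working it through.** **Inputs.** There is no HCU figure in the plan to reproduce. Section 13.2 gives up to 300 subjects as a convenience sample, with no visit rate, dispersion or expected reduction. All rates below are assumptions, and the device effect is set to zero throughout.

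**1. Run-up before prescription.** Let the visit rate in the last 3 months be r times usual, and usual in the other 9 months and in the year after.

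Prior-year total relative to usual = 0.75 + 0.25r

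Apparent change = 1/(0.75 + 0.25r) − 1

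| r (assumed) | Prior-year total | Apparent change |
|---|---|---|
| 1 | 1.000 | 0% |
| 1.5 | 1.125 | −11.1% |
| 2 | 1.250 | −20.0% |
| 3 | 1.500 | −33.3% |

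The total is the same if prescription precedes Day 0 by some weeks at the usual rate, as long as the run-up stays inside the year. Only its position moves.

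**2. Prescribing visit alone.** If a subject's usual count is v per year and the prescribing visit is one extra counted visit, the apparent change is −1/(v + 1): −50% at v = 1, −33% at v = 2, −20% at v = 4. If that visit simply took the place of a routine one, the change is 0%.

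**3. Selection on visits over the whole year.** Let patients have constant rates drawn from a gamma distribution with mean v and shape k, and Poisson counts in each year. If the chance of entry is proportional to the prior-year count, the expected counts are v + v/k + 1 before and v + v/k after. At v = 2 and k = 1 this is 5 against 4, or −20%.

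A simulation with 300 subjects, v from 0.5 to 4 and k from 0.5 to 2 gave no false reduction under unselected entry. False reductions were 4% to 51% when entry needed at least one prior visit, 5% to 63% when it needed at least two, and 8% to 57% with proportional entry.

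Removing 3 months does not cure this kind of selection, because the excess is spread evenly over the year. Nine months hold 5 × 9/12 = 3.75 visits, which annualise to 3.75 × 12/9 = 5, and the change is still −20%.

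**4. Selection on recent visits.** When entry was triggered by visits in the last 3 months (v from 1 to 4, monthly severity autocorrelation 0.5 to 0.95), the false reduction was 11% to 55%. Ending a 12-month comparator 3 months earlier brought it to between −1% and +1%. That result is favourable by construction, since the trigger window was known and severity was stationary. It also used a displaced 12-month window, not an annualised 9-month one.

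**5. Acute-event exclusions.** Section 5.2.2 excludes DVT within 3 months. A DVT 4 months before entry is eligible, and any visits for it can still fall in the prior year.

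**6. Precision of a shorter comparator.** Under constant Poisson rates, the log rate-ratio standard error for 9 against 12 prior months grows by √[(1/12 + 1/9)/(2/12)] = √1.167 = 1.08. If the prescription-to-Day 0 interval also removes 1 or 2 months (assumed), the factor is √[(1/12 + 1/8)/(2/12)] = 1.12 or √[(1/12 + 1/7)/(2/12)] = 1.16.

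**The case against.** A reader might infer that patients are at their worst when the device is prescribed. The documents do not say so. Section 5.2.1 asks only for a prescription, and if prescribing is unrelated to recent visits the run-up component is zero. The exclusions for active infection and for recent DVT, pulmonary embolism or thrombophlebitis also remove some patients near an acute peak. This stands: the range must start at 0%, and the exclusions shrink the effect without removing it.

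A reader might also infer that the endpoint as a whole is biased toward the device. That is not supported either. Prior HCU is recalled once, while on-treatment HCU is asked about at nine contacts, which may raise the later count. Section 7.11.1 counts clinic visits without excluding the five scheduled study visits, whereas the Synopsis speaks of unscheduled visits. If only unscheduled visits were meant, the prescribing visit might not count at all. These points make the net direction uncertain. They do not make an undated total interpretable, because opposing biases of unknown size cannot be assumed to cancel.

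Finally, Section 3.1 says "Therefore we propose to demonstrate improved QoL and symptoms in patients with lower extremity (LE) lymphedema". It is tempting to read this as a claim about HCU, but the sentence concerns quality of life and symptoms. For HCU, Section 4.0 only undertakes to assess and Section 5.1.1 to compare. The point rests on Section 5.1.1.

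That a single arm is an accepted limitation of the design is true, but dating the prior visits needs no control arm.

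**Conclusion.** The concern holds for one component of the HCU comparison. As written, the plan can show a reduction with no device effect: 0%, 11%, 20% or 33% for an assumed final-quarter rate of 1, 1.5, 2 or 3 times usual. A counted prescribing visit that is additional to usual care would add to this. These figures illustrate the mechanism and do not estimate it for this trial, because the documents give no visit rates. Clustering before prescription is an inference, and the net direction of all biases on this endpoint is unknown. The gap worth correcting is that the plan has no means of seeing a run-up or testing how far the result depends on it.

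**What to change.** - **Baseline form (7.2).** Record the date or month of each prior-year HCU visit and the prescription date, and flag the prescribing visit. Dates are needed because Day 0 is not yet known at baseline, so counts in windows before Day 0 cannot be filled in then.
- **Table.** Report HCU rates by quarter before and after Day 0. Contacts at weeks 12, 24, 40 and 52 already bound near-quarterly periods on treatment.
- **Sensitivity analysis (13.1).** Drop the prescribing visit. Compare the on-treatment rate with the annualised prior-year rate after excluding the 3 months before prescription and the prescription-to-Day 0 interval. Report it beside the primary comparison.
- **Interpretation.** State that a single-arm HCU change cannot be attributed to the device alone, and that this analysis does not remove selection on whole-year visit frequency.

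The cost is one or two added baseline fields, some effort to recover dates, and a less precise comparator: about 8% wider on the log rate-ratio standard error for 9 against 12 months, and more if the interval to Day 0 is long.

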5.1.2 Secondary Endpoints

The secondary endpoints for this study will compare changes after 12 and 52 weeks of treatment to baseline for the following:

- Limb circumference
- Skin evaluation

In addition, changes after 24 and 52 weeks of treatment to baseline for the following parameter:

- QoL

To assess Flexitouch compliance, subjects will be categorized as noncompliant, partially compliant, or compliant (Table 1). Primary and secondary outcomes will then be compared across the defined compliance categories.

Table 1. Compliance Category Definitions

Compliance Category	Definition
Noncompliant	Prescribed care followed an average of 0-2 days per week.
Partially Compliance	Prescribed care followed an average of 3-4 days per week.
Compliant	Prescribed care followed an average of 5-7 days per week.

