5.2.3 Subject Withdrawal or Early Termination

Subjects will exit the study if they meet any of the following criteria:

- Subject death
- Subject voluntarily withdraws
- Subject acquires one or more of the exclusion criteria whereby the investigator deems study discontinuation a necessity
 - If subject acquires an infection, they may be treated for the infection and continue in the trial at the investigator’s discretion. Detailed information regarding the infection, nature, treatment, and duration will be recorded.
- Subject diary shows an unwillingness to remain partially compliant or compliant with prescribed care (subject will be considered a screen failure if he or she uses the device <3 times per week on average at the Week 4 visit).

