7.10 Flexitouch Compliance Assessment & Subject Diary

At each phone call and clinic visit, subject compliance will be assessed by collecting the following information:

- Days Flexitouch used in past week
- Days compression garments used in past week
- Difficulty in following treatment
- Difficulty in putting on Flexitouch garments
- Difficulty using Flexitouch controller
- Pain or discomfort experienced when using Flexitouch
- Position treatment being done in

If the subject reports difficulty following treatment, putting on the Flexitouch garment, difficulty using the Flexitouch controller, or is experiencing pain or discomfort when using Flexitouch, the site may refer the subject to Tactile Medical clinical services for assistance in addressing the issue(s).

In addition, the subjects will be provided with a Subject Diary at their Screening/Baseline visit and be instructed to begin completing the diary when they start using their device after their training visit. The subject will be asked to keep a daily record of their use of Flexitouch, Actitouch (if prescribed), and compression stockings. (Appendix C) Subjects should bring their diary into each study visit for review and collection.

If the subject is noncompliant or partially compliant in device use, (see Table 1), the site should identify barriers to compliance and determine if additional device training by the site or Tactile personnel is warranted. If noncompliance continues, the Investigator may initiate the subject's withdrawal from the study.

At the 4 week in-clinic follow-up visit, if a subject is not using their Flexitouch an average of 3 times per week, they will be considered a screen failure.

If the subject experiences a complication (e.g., active infection, DVT) that requires temporary discontinuation of device use and 4 weeks of continuous treatment is not possible before the final in-clinic visit takes place, the subject should be withdrawn from the study.

Additionally, a device history log may be downloaded periodically from Flexitouch Plus units.

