7.11.1 Lymphedema and Venous Related HCU

Lymphedema and venous related visits that required HCU (includes clinic visits, hospitalization, walk-in clinic/urgent care, and ER visits).

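### Comparing 52-week health care utilization across compliance categories can favour the device with no true effect, because complications also interrupt device use

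*Combined protocol and SAP*

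**What the plan says.** Table 1 in Section 5.1.2 defines compliant as "Prescribed care followed an average of 5-7 days per week" and partially compliant as "Prescribed care followed an average of 3-4 days per week". No averaging window is given. The section then states: "Primary and secondary outcomes will then be compared across the defined compliance categories".

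The outcomes include two kinds of primary endpoint (Section 5.1.1). For quality of life (QoL) and symptoms the plan "will compare changes after 12 weeks of treatment to baseline". For HCU, "the number of occurrences after 52 weeks of treatment will be compared to the number of occurrences in the year preceding treatment". Section 7.11.1 defines HCU as "Lymphedema and venous related visits that required HCU (includes clinic visits, hospitalization, walk-in clinic/urgent care, and ER visits".

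Section 7.10 has a rule that begins: "If the subject experiences a complication (e.g., active infection, DVT) that requires temporary discontinuation of device use". It withdraws the subject only if four weeks of continuous treatment no longer fit before the last clinic visit. Section 5.2.3 says of subjects who acquire an infection that "they may be treated for the infection and continue in the trial", at the investigator's discretion. Section 13.1 names no method and no rule for interrupted weeks.

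**The concern.** Read together, these sections let a single event act on both sides of the comparison. An infection or a DVT is likely to lead to a visit that counts as HCU. The same event can take the subject off the device for some weeks, which lowers average days per week and may move the subject out of the compliant category. Causation then runs from outcome to compliance, and the resulting bias always favours the device.

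In a single-arm study, this is the only planned internal comparison by amount of use. A lower HCU rate among compliant subjects could easily be read as evidence of benefit when part or all of it comes from how the categories were formed.

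**Working it through.** The plan gives no figure to reproduce. It states no visit rate, no share of visits that interrupt use and no interruption length, so every size below rests on stated assumptions, with no device effect built in.

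**1. How easily a category changes.** A subject who uses the device u days a week falls below 5 on average after period × (1 − 5/u) weeks off. For u = 6:
- 52-week average: 52 × (1 − 5/6) = 8.7 weeks off
- 12-week average: 12 × (1 − 5/6) = 2.0 weeks off

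Subjects nearer the boundary need less.

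**2. Size by share of visits that interrupt use.** Assumptions:
- 300 subjects per trial
- HCU gamma-Poisson, mean 2 visits a year, shape 2, so some subjects are more prone to visits than others
- usual use 7 × Beta(4,2) days a week, independent of visit risk
- compliant means an average of at least 4.5 days (Table 1 leaves averages between 4 and 5 unassigned)
- Week 4 screen-failure rule applied

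| Visits that interrupt use | Weeks off | HCU ratio, compliant vs rest (truth 1.00) |
|---|---|---|
| 10% | 2 | 0.97 |
| 20% | 4 | 0.84 |
| 50% | 4 | 0.64 |
| 100% | 4 | 0.42 |

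**3. A second model with different assumptions.** Complications occur at 0.2, 0.5 or 1.0 a year. Each adds one visit to a background of one visit a year that does not affect use. Usual use is about Normal(5.5, 1.2) days a week and the cut is at 5 days. The Week 4 and late-withdrawal rules are applied, with 600 trials of 300 subjects per scenario. Each cell gives the HCU ratio and the share of trials with a false significant result favouring compliant subjects (nominal 2.5%), when all subjects share the same complication risk.

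| Complications per year | 2 weeks off | 4 weeks off | 8 weeks off |
|---|---|---|---|
| 0.2 | 0.96 (4.8%) | 0.92 (8.3%) | 0.85 (26%) |
| 0.5 | 0.94 (7.2%) | 0.84 (35%) | 0.73 (81%) |
| 1.0 | 0.89 (22%) | 0.77 (77%) | 0.63 (99.5%) |

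With complication risk varying between subjects, the ratios run from 0.96 to 0.59. With no complications the ratio is 1.00, so the interruptions are the cause.

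**4. Week 12 QoL.** In the second model, assuming a loss of 0.5 SD when a complication falls in Weeks 9-12, the spurious difference is 0.01 to 0.06 SD, with 3% to 7% false significant results.

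**5. What removes the bias.**
- *Average only over uninterrupted weeks, same 52 weeks:* ratio 1.00 to 1.03 in the second model, with false results near or below nominal. In the first model it is about 1.01 to 1.07, with or without a landmark, so the small remainder does not favour the device.
- *Landmark alone (compliance from Weeks 1-12, HCU afterwards, interruptions counted as nonuse):* about 0.78 to 1.00 in the first model. In the second model it is 1.00 to 1.01 with equal risk, but 0.89 to 0.99, with up to 12.3% false results, when risk varies.

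Time order alone fails because complication-prone subjects are interrupted early and also have more visits later.

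**The case against.** **The same-period reading is inferred.** True: Section 5.1.2 gives no window. But the diary is kept to Week 52 and Table 1 speaks of an average, so this is the natural reading. The missing window is itself part of the gap.

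**A clinician-ordered pause may count as following prescribed care.** Table 1 could be read so, which would weaken the mechanism. Section 7.10, however, cites Table 1 when it speaks of compliance in device use, and Section 5.2.3 applies a device-use threshold. The text does not settle the matter.

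**Many HCU visits will not stop the device.** This stands. HCU includes ordinary clinic visits, and Section 7.10 ties interruption to complications only. The bias could be negligible, and the severe end of the range should not be quoted alone.

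**Existing rules already limit the problem.** Only slightly. In the second model at 0.5 complications a year and 4 weeks off, false results fall from 42% to 35% with the late-withdrawal rule.

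**Adherers differ from non-adherers anyway.** They do, and no rule for interrupted weeks cures that. Reverse causation is a separate problem, and it can be removed.

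**Conclusion.** The point holds for the 52-week HCU comparison across compliance categories. Followed as written, and on the natural reading of the window, the plan can show a benefit that does not exist. The direction is fixed; the size is not. The spurious ratio runs from about 0.97 to 0.42 over the tabulated cases at an assumed 2 visits a year, depending on inputs that the documents do not give.

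A reader might infer three stronger things that the documents do not support:
- *That the bias is certain to be large.* With rare, short interruptions it is close to nothing.
- *That all outcomes are affected alike.* Week 12 QoL is barely moved under the assumptions tried.
- *That the primary results are compromised.* The before-after contrasts in Section 5.1.1 do not use the compliance categories, and Section 5.1.2 introduces this secondary comparison as a way to assess compliance, not as evidence of efficacy.

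**What to change.** For the HCU comparison in Section 5.1.2, state in the SAP:

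1. The averaging window for compliance.
2. That average use is computed only over weeks in which the device was not stopped for a medical reason. Date those stops from the HCU records (Section 7.11), infection details (Section 5.2.3) and prescribed-care review (Section 7.7), read together with the daily diary.
3. As a sensitivity analysis, classify subjects on Weeks 1-12, again leaving out interrupted weeks, and compare HCU in Weeks 13-52. Do not use a landmark that counts interruptions as nonuse.
4. That all comparisons across compliance categories are reported as associations.

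The cost is SAP wording plus a derivation rule. The main analysis keeps all 52 weeks of HCU; only the sensitivity analysis gives up the first 12.

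The weak spot is the dating. The diary in Appendix C records which treatments were used, but not why one was missed, and contacts are up to 12 weeks apart (Week 40 to Week 52). Some medical stops may be dated imprecisely unless a stop and restart date is added to the existing compliance form. The device log mentioned in Section 7.10 may help to locate gaps in use, but its download is optional and it is described only for Flexitouch Plus units.
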